8.5.3 Subgroup analysis

Not applicable.

8.5.4 Interim analysis

No interim analyses are planned.

8.5.5 Sensitivity analysis

Sensitivity analysis of the primary variable will be carried out and will be specified in the SAP.

8.5.6 Exploratory analysis

Not applicable.

9. STUDY AND DATA MANAGEMENT BY ASTRAZENECA

9.1 Training of study site personnel

Before the first subject is entered into the study, an AstraZeneca representative will review and discuss the requirements of the Clinical Study Protocol and related documents with the investigational staff and also train them in any study specific procedures and system(s) utilised.

The Principal Investigator will ensure that appropriate training relevant to the study is given to all of these staff, and that any new information relevant to the performance of this study is forwarded to the staff involved.

The Principal Investigator will maintain a record of all individuals involved in the study (medical, nursing and other staff).

9.2 Monitoring of the study

During the study, an AstraZeneca representative will have regular contacts with the study site, including visits to:

- Provide information and support to the Investigator(s)
- Confirm that facilities remain acceptable
- Confirm that the investigational team is adhering to the protocol, that data are being accurately and timely recorded in the CRFs, that biological samples are handled in accordance with the Laboratory Manual and that study drug accountability checks are being performed
- Perform source data verification (a comparison of the data in the CRFs with the subject's medical records at the hospital or practice, and other records relevant to the study) including verification of informed consent of participating subjects. This will require direct access to all original records for each subject (e.g., clinic charts)
- Ensure withdrawal of informed consent to the use of the subject's biological samples is reported and biological samples are identified and disposed of/destroyed accordingly, and the action is documented, and reported to the subject.

The AstraZeneca representative will be available between visits if the Investigator(s) or other staff at the centre needs information and advice about the study conduct.

9.2.1 Source data

Original patient data in study sites

9.2.2 Study agreements

The Principal Investigator at each/the centre should comply with all the terms, conditions, and obligations of the Clinical Study Agreement, or equivalent, for this study. In the event of any inconsistency between this Clinical Study Protocol and the Clinical Study Agreement, the terms of Clinical Study Protocol shall prevail with respect to the conduct of the study and the treatment of subjects and in all other respects, not relating to study conduct or treatment of subjects, the terms of the Clinical Study Agreement shall prevail.

Agreements between AstraZeneca and the Principal Investigator should be in place before any study-related procedures can take place, or subjects are enrolled.

9.2.3 Archiving of study documents

The Investigator follows the principles outlined in the Clinical Study Agreement (CSA).

9.3 Study timetable and end of study

The end of the study is defined as ‘the last visit of the last subject undergoing the study’.

The study is expected to start in Q4 2015 and to end by Q2 2017

The study may be terminated at individual centres if the study procedures are not being performed according to GCP, or if recruitment is slow. AstraZeneca may also terminate the entire study prematurely if concerns for safety arise within this study or in any other study with dapagliflozin.

9.4 Data management by delegate of AstraZeneca

Data management will be performed by CRO, according to the Data Management Plan. Adverse events and medical/surgical history will be classified according to the terminology of the latest version the Medical Dictionary for Regulatory Activities (MedDRA). Medications will be classified according to the AstraZeneca Drug Dictionary. Classification coding will be performed by CRO.

The data collected through third party sources will be obtained and reconciled against study data.

Data queries will be raised for inconsistent, impossible or missing data. All entries to the study database will be available in an audit trail.

The data will be validated as defined in the Data Management Plan. Quality control procedures will be applied to each stage of data handling to ensure that all data are reliable and have been processed correctly. The Data Management Plan will also clarify the roles and responsibilities of the various functions and personnel involved in the data management process

When all data have been coded, validated, <<signed>> and locked, clean file will be declared. Any treatment revealing data may thereafter be added and the final database will be locked.

Serious Adverse Event (SAE) Reconciliation

SAE reconciliation reports are produced and reconciled with the Patient Safety database and/or the investigational database.

Data Management of genotype data

Not applicable.

10. ETHICAL AND REGULATORY REQUIREMENTS

10.1 Ethical conduct of the study

The study will be performed in accordance with ethical principles that have their origin in the Declaration of Helsinki and are consistent with ICH/Good Clinical Practice, applicable regulatory requirements and the AstraZeneca policy on Bioethics and Human Biological Samples.

10.2 Subject data protection

The Informed Consent Form will incorporate wording that complies with relevant data protection and privacy legislation.

- Study data will be stored in a computer database, maintaining confidentiality in accordance with relevant data protection and privacy legislation
- Patient data will be maintaining confidentiality in accordance with relevant data protection and privacy legislation
- For data verification purposes, authorised representatives of AstraZeneca, a regulatory authority, an IRB may require direct access to parts of the hospital or practice source records relevant to the study, including subjects' medical history
- All data computer processed by AstraZeneca will be identified by study code and enrolment code (E-code)

10.3 Ethics and regulatory review

An Institutional Review Board (IRB) should approve the final study protocol, including the final version of the Informed Consent Form and any other written information and/or materials to be provided to the subjects. The Investigator will ensure the distribution of these documents to the applicable IRB, and to the study site staff.

The opinion of the IRB should be given in writing. The Investigator should submit the written approval to AstraZeneca before enrolment of any subject into the study.

The IRB should approve all advertising used to recruit subjects for the study.

AstraZeneca should approve any modifications to the Informed Consent Form that are needed to meet local requirements.

Before enrolment of any subject into the study, the final study protocol, including the final version of the Informed Consent Form, is approved by the national regulatory authority or a notification to the national regulatory authority is done, according to local regulations.

AstraZeneca will handle the distribution of any of these documents to the national regulatory authorities.

AstraZeneca will provide Regulatory Authorities, IRB and Principal Investigators with safety updates/reports according to local requirements.

10.4 Informed consent

The Principal Investigator(s) at each centre will:

- Ensure each subject is given full and adequate oral and written information about the nature, purpose, possible risk and benefit of the study
- Ensure each subject is notified that they are free to discontinue from the study at any time
- Ensure that each subject is given the opportunity to ask questions and allowed time to consider the information provided
- Ensure each subject provides signed and dated informed consent before conducting any procedure specifically for the study
- Ensure the original, signed Informed Consent Form(s) is/are stored in the Investigator's Study File
- Ensure a copy of the signed Informed Consent Form is given to the subject
- Ensure that any incentives for subjects who participate in the study as well as any provisions for subjects harmed as a consequence of study participation are described in the informed consent form that is approved by an Ethics Committee.

The environment where the process of consent is conducted should be determined by the type of research being conducted but there should always be a period where a private, confidential, and "safe" setting is afforded to facilitate a constructive dialogue between the prospective subject and the person(s) involved in obtaining consent.

10.5 Changes to the protocol and informed consent form

Study procedures will not be changed without the mutual agreement of the Principal Investigator and AstraZeneca.

If there are any substantial changes to the study protocol, then these changes will be documented in a study protocol amendment and where required in a new version of the study protocol (Revised Clinical Study Protocol).

The amendment is to be approved by the relevant IRB and if applicable, also the national regulatory authority approval, before implementation. Local requirements are to be followed for revised protocols.

AstraZeneca will distribute any subsequent amendments and new versions of the protocol to each Principal Investigator(s). For distribution to IRB see Section 10.3.

If a protocol amendment requires a change to a centre's Informed Consent Form, AstraZeneca and the centre's IRB are to approve the revised Informed Consent Form before the revised form is used.

If local regulations require, any administrative change will be communicated to or approved by each Ethics Committee.

Authorised representatives of AstraZeneca, a regulatory authority, or an Ethics Committee may perform audits or inspections at the centre, including source data verification. The purpose of an audit or inspection is to systematically and independently examine all study-related activities and documents, to determine whether these activities were conducted, and data were recorded, analysed, and accurately reported according to the protocol, Good Clinical Practice (GCP), guidelines of the International Conference on Harmonisation (ICH), and any applicable regulatory requirements. The Investigator will contact AstraZeneca immediately if contacted by a regulatory agency about an inspection at the centre.

Appendix A Additional Safety Information

Further Guidance on the Definition of a Serious Adverse Event (SAE)

Life threatening

‘Life-threatening’ means that the subject was at immediate risk of death from the AE as it occurred or it is suspected that use or continued use of the product would result in the subject’s death. ‘Life-threatening’ does not mean that had an AE occurred in a more severe form it might have caused death (eg, hepatitis that resolved without hepatic failure).

Hospitalisation

Outpatient treatment in an emergency room is not in itself a serious AE, although the reasons for it may be (eg, bronchospasm, laryngeal oedema). Hospital admissions and/or surgical operations planned before or during a study are not considered AEs if the illness or disease existed before the subject was enrolled in the study, provided that it did not deteriorate in an unexpected way during the study.

Important medical event or medical intervention

Medical and scientific judgement should be exercised in deciding whether a case is serious in situations where important medical events may not be immediately life threatening or result in death, hospitalisation, disability or incapacity but may jeopardize the subject or may require medical intervention to prevent one or more outcomes listed in the definition of serious. These should usually be considered as serious.

Simply stopping the suspect drug does not mean that it is an important medical event; medical judgement must be used.

- Angioedema not severe enough to require intubation but requiring iv hydrocortisone treatment
- Hepatotoxicity caused by paracetamol (acetaminophen) overdose requiring treatment with N-acetylcysteine
- Intensive treatment in an emergency room or at home for allergic bronchospasm
- Blood dyscrasias (eg, neutropenia or anaemia requiring blood transfusion, etc) or convulsions that do not result in hospitalisation

Development of drug dependency or drug abuse

A Guide to Interpreting the Causality Question

When making an assessment of causality consider the following factors when deciding if there is a ‘reasonable possibility’ that an AE may have been caused by the drug.

- Time Course. Exposure to suspect drug. Has the subject actually received the suspect drug? Did the AE occur in a reasonable temporal relationship to the administration of the suspect drug?

---

## LIST OF ABBREVIATIONS

Abbreviation or special term	Explanation
A1C	Glycated hemoglobin
AE	Adverse Event
ALT	Alanine Aminotransferase
AST	Aspartate Aminotransferase
BMI	Body Mass Index
BMS	Bristol-Myers Squibb
BP	Blood Pressure
CBC	Complete Blood Count
CK	Creatinine Kinase
CPMP	Committee for Proprietary Medicinal Products (EU)
CRF	Case Report Form
CRO	Clinical Research Organization
CSA	Clinical Study Agreement
CSR	Clinical Study Report
CT	Computerized Tomography
DNA	Deoxyribonucleic Acid
DTSQ	Diabetes Treatment Satisfaction Questionnaire
DTSQc	DTSQ Change Version
DTSQs	DTSQ Status Version
DXA	Dual Energy Xray Absorptiometry

Abbreviation or special term	Explanation
ECG	Electrocardiogram
eCRF	Electronic Case Report Form
Ethics Committee	Synonymous to Institutional Review Board and Independent Ethics Committee
FDA	Food and Drug Administration (US)
FFA	Free Fatty Acid
FBG	Fasting Blood Glucose
FSH	Follicle-stimulating Hormone
GCP	Good Clinical Practice
GMP	Good Manufacturing Practice
HDL-C	High-density Lipoprotein Cholesterol
HRT	Hormone replacement Therapy
ICH	International Conference on Harmonisation
IPS	Investigational Products
LDL-C	Low-density Lipoprotein Cholesterol
LOCF	Last Observation Carried Forward
N.B.	Nota Bene, mind you
OAD	Oral Antidiabetic Drug
pCRF	Paper Case Report Form
PK	Pharmacokinetics
PPG	Postprandial Plasma Glucose
PPG AUC	Postprandial Glucose Area Under the Curve

Abbreviation or special term	Explanation
PRO	Patient-reported Outcome
SAE	Serious Adverse Event (see definition in Section6.9).
SAT	Subcutaneous adipose tissue
SDT	Study Delivery Team
SGLT1	Sodium-dependent Glucose Transporter 1
SGLT2	Sodium-dependent Glucose Transporter 2
SU	Sulphonylurea(s)
TG	Triglyceride
TSH	Thyroid-stimulating Hormone
T2DM	Type 2 Diabetes Mellitus
UACR	Urine Albumin:Creatinine Ratio
ULN	Upper Limit of Normal
VAT	Visceral adipose tissue
WBDC	Web Based Data Capture
WOCBP	Women of child bearing potential

## AMENDMENT HISTORY

---

Date	Brief description of change
11Jan2016	N/A First Version
24AUG2017	Sensitivity Analysis are added as supportive analysis to assess the impact on gender ratio on primary and secondary endpoints.

---

## 1. STUDY DETAILS

This statistical analysis plan (SAP) provides a detailed description of the statistical methods proposed in the study protocol 08 February 2018 dated on 07JUN2016 version 3.

### 1.1 Study objectives

The primary objective of the study is to evaluate the effect of Dapagliflozin compared to Glimepiride on body composition in Korean Type 2 Diabetes Mellitus (T2DM) subjects, by assessing the changes in total body fat mass from baseline using DXA scan in 52 weeks after the start of the treatment.

There are multiple secondary objectives in this study;

To evaluate the efficacy in improving glycaemic control of Dapagliflozin compared to Glimepiride in subjects with type 2 diabetes by following assessments:

- The change in HbA1c levels from baseline to 52 weeks (baseline, 12, 24, 36 and 52 weeks)
- The proportion of subjects achieving a glycemic response, defined as HbA1c <7.0% at Week 52
- The change in FBS levels from baseline to 52 weeks (baseline, 4, 12, 24, 36 and 52 weeks)

To evaluate the effect on body weight of Dapagliflozin compared to Glimepiride in subjects with type 2 diabetes, by assessing changes in body weight, waist circumference, BMI from baseline to 4, 12, 24, 36 and 52weeks.

To evaluate the effect on blood pressure of Dapagliflozin compared to Glimepiride in subjects with type 2 diabetes, by assessing changes in SBP and DBP from baseline 4, 12, 24, 36 and 52weeks.

To evaluate the effect on adipose tissue and lean volume of Dapagliflozin compared to Glimepiride in subjects with type 2 diabetes, by assessing changes in abdominal VAT and SAT area, VAT/SAT ratio using abdominal CT from baseline to 52 weeks (baseline, 52 weeks) and changes in lean mass from baseline using Dual Energy X-ray Absorptiometry (DXA) scan to 52 weeks (baseline, 52 weeks).

To evaluate the effect on insulin resistance of Dapagliflozin compared to Glimepiride in subjects with type 2 diabetes, by assessing changes in high-sensitivity CRP (hsCRP) and adiponectin from baseline to 52 weeks (baseline, 52 weeks).

To evaluate the safety of Dapagliflozin and Glimepiride, by following assessments:

[figure not shown]
- Changes in CBC, electrolytes, lipid, urinalysis from baseline to 4, 12, 24, 36 and 52weeks

- Number, frequency and proportion of subjects exposed to adverse events
- Number, frequency and proportion of subjects exposed to hypoglycemic events

## 1.2 Study design

This is a 52 weeks, randomized, open-label, parallel-group, multi-centres phase IV study to evaluate the effects of Dapagliflozin compared with Glimepiride on body composition in patients with Type 2 Diabetes inadequately controlled with Metformin. 120 participants will be randomized 1:1 to receive Dapagliflozin 10 mg qd or Glimepiride 1~2 mg qd in an open-label manner for 12 months as add-on to Metformin 1000 mg. The study design and plan are summarized in Figure 1 below and Table 1 in study protocol.

Figure 1 Study Flow Chart

Scheduled visits of the study include measurements at baseline, 4, 12, 24, 36 and 52 weeks. Subjects with T2DM and inadequate glycaemic control ( $HbA1c \geq 7.5\%$  and  $\leq 9.5\%$ ) having stable Metformin monotherapy  $\geq 1000$  mg/day for at least 8 weeks prior to enrolment will be eligible to enter the study. Subjects early terminate or complete study treatment will not be further followed after End of Treatment (EoT) Visit. Table 1 in study protocol provides a detailed schedule of assessments of events related to the study objective.

## 1.3 Number of subjects

To evaluate the effect of Dapagliflozin on body composition in Korean T2DM subjects:

Redacted

[Redacted text block]

[Redacted text block]

[Redacted text block]

## **2. ANALYSIS SETS**

### **2.1 Definition of analysis sets**

Patient inclusion in each of the analysis sets will be finalised prior to database lock. For analyses and displays based on Safety Analysis Set (SAF), subjects will be classified according to the actual treatment they received. All other analyses will be performed based on treatment group to which subjects were randomized.

#### **2.1.1 All Patients Enrolled Set [ENR]**

The all patients enrolled (ENR) set will include all patients who gave consent to participate in the study.

#### **2.1.2 All Subjects Randomized Set [RND]**

The all subjects randomized (RND) set will contain all subjects in the ENR set who were randomized to one of the treatment arms.

#### **2.1.3 Safety Analysis Set [SAF]**

The safety analysis set [SAF] will include all RND subjects who received at least one dose of study medication during treatment period.

If there is any doubt whether a subject was treated or not, they will be assumed treated for the purposes of analysis.

For analyses based on SAF, subjects who were dispensed with the wrong treatment (treatment other than the one they are randomized to) will be counted in the treatment group for which they actually received medication.

#### **2.1.4 Full Analysis Set [FAS]**

The full analysis set [FAS] will include all RND subjects who received at least one dose of study medication during the 52 week treatment period and have a non-missing baseline value and at least one post-baseline value for primary efficacy variable (total body fat mass).

Whenever using the FAS, subjects will be presented in the treatment group to which they were randomized.

#### **2.1.5 Per-Protocol Set [PPS]**

The per-protocol set [PPS] is a subset of the FAS consisting of subjects who do not violate the terms of the protocol, which may affect the efficacy endpoints significantly (relevant protocol deviators).

All decisions to exclude subjects from the FAS set to create the PPS set will be made prior to DB locking.

Whenever using the PPS, subjects will be presented in the treatment group to which they were randomized.

## 2.2 Violations and deviations

Protocol deviations (PDs) will be identified via programming to complement protocol deviation log. If a patient meets any of the following criteria, the patient will be reviewed and may be considered to be a relevant deviator, and consequently all data for that patient will be excluded from the PPS population. All relevant and irrelevant major/critical protocol deviations will be tabulated and listed and will include, but will not be limited to;

- Patients failing to meet inclusion/exclusion criteria but mistakenly randomized.
- Randomized patients who failed to receive treatment.
- Prohibited concomitant medications.
- Receiving wrong treatment.
- Developing withdrawal criteria whilst on the study but are not withdrawn;

Patients with poor treatment compliance are defined as those taking < 80% or > 120% of planned Investigating Product (IP). Treatment compliance algorithm will be discussed in a separate section.

A list of prohibited concomitant medications is provided in the study protocol, Section 6.15.2. Correspond drug names is listed in the [Appendix 1](#) of the SAP.

If a patient satisfies more than one of the reasons for protocol deviation listed above, and is judged to have both relevant and irrelevant deviations, then s/he will be defined as a relevant deviator. For tabulation purposes s/he will be counted as a relevant deviator once overall, but also once within each deviation reason.

As drug dispense/return/lost information is not captured on CRF, calculated poor compliance defined above will be programmed to compare with poor treatment compliance reported in the PD log.

## 3. A LIST OF MINOR PROTOCOL DEVIATIONS WILL ALSO BE PROVIDED. ANALYSIS METHODS

Statistical summaries will be performed by QuintilesIMS using SAS version 9.2 (or higher) and where appropriate, additional validated software.

### **3.1 General Principles**

All safety outcome summaries will be performed on the SAF whilst all efficacy analyses will be performed on FAS or PPS (PPS for sensitivity analyses of efficacy endpoints) unless otherwise stated. In addition to the formal presentation of results detailed in the following sections, all study data will be listed by centre, patient number and treatment group.

For continuous data, descriptive statistics will be presented for each treatment group and overall, which includes number of patients (n), mean, SD, median, maximum and minimum unless otherwise specified.

For categorical data, the frequency and percentage of patients in each category will be presented. Counts that are zero will be displayed as “0” and all percentages will be based on population size of each treatment group unless otherwise specified.

Data will be listed to the same accuracy as recorded in the eCRF. Mean and median summary statistics will be presented to one additional decimal place, whilst the standard deviation (SD) will be presented to two additional decimal places. Minimum and maximum values will be presented to the same accuracy as recorded on the eCRF.

The default significant level of statistical testing will be 5%; confidence intervals will be two-sided 95% and all tests will be two-sided, unless otherwise specified in the description of the analyses.

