### **3.8.3 Sensitivity Analysis of Secondary Endpoints**

To assess the robustness of the missing data imputation (LOCF), the same model and statistics will be generated for FAS population with only truly observed data when evaluating proportion of subjects achieving a glycemic response.

To evaluate the impact of protocol compliance on secondary efficacy endpoint, secondary efficacy models (with imputed data for glycemic response) method will be repeated on the PPS population.

To evaluate the impact of gender ratio on secondary efficacy endpoints, the secondary endpoints will be analyzed as a sensitivity analysis by a mixed model for repeated measures (MMRM) where all post-baseline secondary endpoints (HbA1c levels, FBS levels, body weight, waist circumference, BMI, SBP and DBP) obtained at all planned visits before discontinuation from randomized treatment and visit and treatment are included as fixed factors and Baseline secondary endpoints and gender as covariates. Furthermore, interaction terms of visit by treatment, visit by gender and visit by respective Baseline secondary

endpoints will be included. An unstructured covariance matrix for respective Baseline secondary endpoint measurements within same patient will be employed. Regarding missing data this analysis approach relies on the assumption that data are missing at random. The estimated differences between each treatment groups at Week 52 and corresponding two sided p-values and 95% CI will be presented.

To evaluate the impact of gender ratio on secondary efficacy endpoint VAT/SAT area, VAT/SAT ratio and total body lean mass, these parameters will be analysed using ANCOVA model with treatment group as factor and Baseline test results and gender as a covariate on FAS and PPS population. The statistical modelling and analysis will be performed in the same manner as the primary efficacy variable using an ANCOVA model (Sensitivity Analysis).

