### 3.9.3 Laboratory Evaluations

Results from the central laboratory will be included in the reporting for serum chemistry, hematology and urinalysis. A list of tests to be performed is included in Protocol section 5.2.1.

The following summaries will be provided for laboratory data:

- Actual value of each scheduled visit and change from baseline for each post-baseline scheduled measurement by visit (for quantitative measurements only).
- Incidence of abnormal values according to normal range criteria. Abnormalities will be classified to “Low” if smaller than the lower limit while “High” if larger than the upper limit.
- Shift from baseline according to abnormality status (Low, Normal and High) for each post-baseline scheduled measurement. For urinalysis, shift between normal and abnormal will be prepared.
- Listing of observed results for all laboratory values will be provided with abnormality status flagged.

- Additionally, Change from screening (visit 1) to each post-treatment time point will be reported for CBC, electrolytes, lipid parameters.

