### **3.9.4 ECG Evaluations**

ECG results will be captured on CRF page “pECG” and will contain overall assessment based on Investigator’s judgment:

- Normal
- Abnormal, Not Clinically Significant (ANCS)
- Abnormal, Clinically Significant (ACS)

For baseline and each post-baseline measurement, the numbers and percentages of patients in each category above will be summarized.

In addition, heart rate, PR interval, QRS interval and QT interval will be summarized and listed for SAF set.

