### **3.9.6 Physical Examinations**

A physical examination will include an assessment of the following: general appearance, respiratory, cardiovascular, abdomen, head and neck (including head, ears, eyes, nose and throat).

Findings in each body system tested will be summarized for all scheduled visits. The examination at visit 1 will be considered as baseline and change from baseline will be calculated for the following visits.

All physical examination results will be listed for SAF set.

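### SAP 3.1 makes arm size the default denominator, so laboratory shift and physical examination percentages at intermediate visits count subjects with no value, and fall as subjects leave

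*SAP*

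**What the plan says.** SAP 3.1 asks for a frequency and a percentage for categorical data and fixes the denominator by default: "all percentages will be based on population size of each treatment group unless otherwise specified". Safety summaries use the safety analysis set, which under SAP 2.1.3 requires only one dose of study medication.

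Two safety sections then describe categorical results at successive visits:

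- SAP 3.9.3 plans "Shift from baseline according to abnormality status (Low, Normal and High) for each post-baseline scheduled measurement", with a normal/abnormal version for urinalysis.
- SAP 3.9.6 states: "Findings in each body system tested will be summarized for all scheduled visits".

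Neither gives a denominator or a row for missing values.

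SAP 3.1.3 says that subjects who stop treatment early have the Visit 7 assessments, are not followed after that, and have those results presented with the End of Treatment visit.

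**The concern.** A subject who stops at, say, Week 16 has no laboratory or examination result at Weeks 24 and 36, but still belongs to the safety set. If the arm size is the denominator at those visits, that subject counts as someone without the finding.

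This has three consequences:

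- The percentage abnormal drifts down as subjects leave, with no change in the subjects who are measured.
- If the arms lose subjects at different rates, equal rates among those measured print as unequal, or a real difference is hidden. Unequal loss is plausible here. Protocol 3.9 and 4.3 link discontinuation to major or recurring minor hypoglycaemia. Protocol 1.1 describes hypoglycaemia as a frequent problem with sulfonylureas, and Protocol 1.3 describes a low risk with dapagliflozin.
- Low, Normal and High do not add to 100% at a visit, and no stated row accounts for the remainder. The mean of the same test at the same visit rests on the n measured, because SAP 3.1 requires n for continuous summaries.

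These tables are a main display of categorical laboratory and examination safety data in an open-label comparison, and no model behind them corrects the denominator.

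**Working it through.** The plan states no figure on this point to reproduce. The sample-size sections are redacted, so any dropout allowance there cannot be seen; the missing shares below are assumptions.

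**Inputs**

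- Arm size N: about 60, from 120 randomised 1:1 (SAP 1.2). The safety set could be slightly smaller; N cancels in the formula.
- p: the percentage with the finding among subjects measured at the visit (illustrative values).
- m: the share of the arm with no value at that visit (assumed, 0 to 25%).

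**Formula**

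Number measured = N(1 − m). Number with the finding = p × N(1 − m). Printed percentage under the default = p × N(1 − m) / N = p(1 − m).

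**Results**

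| Assumed m | Measured, N = 60 | p = 10% prints as | p = 20% prints as | p = 40% prints as |
|---|---|---|---|---|
| 0% | 60 | 10.0% | 20.0% | 40.0% |
| 5% | 57 | 9.5% | 19.0% | 38.0% |
| 10% | 54 | 9.0% | 18.0% | 36.0% |
| 20% | 48 | 8.0% | 16.0% | 32.0% |
| 25% | 45 | 7.5% | 15.0% | 30.0% |

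**Unequal loss.** With m = 5% in one arm and 20% in the other, and p = 20% in both: 0.20 × 0.95 = 19% against 0.20 × 0.80 = 16%. The 3-point gap comes from the denominator alone.

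**Sum of categories.** At m = 20%, Low + Normal + High = 100% × (1 − 0.20) = 80%.

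**Pattern over visits.** Early-exit results are shown at End of Treatment, so m should be near zero there and largest at the last intermediate visit. If m were 5%, 10% and 20% at Weeks 12, 24 and 36 and 0% at End of Treatment, a constant p = 20% would print as 19%, 18%, 16% and then 20%. That dip and recovery would be an artefact.

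**Where the rule bites**

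| Summary | By visit at intermediate visits? | Denominator in its own section | Default distorts it? |
|---|---|---|---|
| Laboratory and urinalysis shift (SAP 3.9.3) | Yes | None | Yes, if values are missing |
| Physical examination (SAP 3.9.6) | Yes | None | Yes, if values are missing |
| ECG (SAP 3.9.4) | No: Visits 1 and 7 only (Protocol 4.1, 4.4) | None | Little; exit data join End of Treatment |
| Incidence of abnormal laboratory values (SAP 3.9.3) | Not described as by visit | None | Arm size is a usual choice for an any-time incidence |
| Observed-data glycaemic response (SAP 3.8.3) | Week 52 only | Restricted to observed data | Odds ratio unaffected |

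**The case against.** The strongest reply is that this is a display convention. Counts accompany the percentages, n is given for the quantitative tests, and SAP 3.9 plans no between-arm test on safety data except for hypoglycaemic events, where arm size is the right denominator. SAP 3.1 also allows exceptions, and SAP 3.9.1 refers to output templates that are not in these documents; templates for other tables may set another denominator or add a missing row. This limits the consequence but does not remove the gap. A count and a stated rule still yield a percentage that falls with dropout, and nothing in the SAP text overrides that rule for the shift and examination tables.

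A reader might also infer more than the documents support:

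- **That every percentage in the report is too low.** The default gives way where another basis is specified, it suits any-time incidence tables, and it does no harm where all subjects are measured. SAP 3.9.3 lists "Incidence of abnormal values according to normal range criteria" without describing it as by visit.
- **That the ECG table is badly affected.** SAP 3.9.4 speaks of each post-baseline measurement, but the only scheduled one is at Visit 7. Protocol 3.9.1 asks early leavers to complete the Visit 7 procedures, and SAP 3.1.3 shows those data with End of Treatment. Only subjects who miss the exit visit would be absent.
- **That the observed-data responder analysis contradicts its own odds ratio.** SAP 3.8.3 says "the same model and statistics will be generated for FAS population with only truly observed data", which is itself a different specification. The odds ratio does not depend on a printed denominator, and that section names no separate table of counts and percentages. Nor should much be missing: the full analysis set needs a post-baseline DXA (SAP 2.1.4), which is done at Visit 7 or the exit visit, when HbA1c is also drawn (Protocol 4.4).

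**Conclusion.** The point holds for the laboratory and urinalysis shift tables and the physical examination findings at intermediate scheduled visits. Read as written, SAP 3.1 keeps unmeasured subjects in those denominators and scales the printed percentage by (1 − m).

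For assumed m of 5% to 25%, the relative reduction is 5% to 25%: 0.5 to 2.5 points at a measured 10%, and 2 to 10 points at a measured 40%. It is zero at m = 0. A spurious arm difference also requires unequal missing shares, which the discontinuation rules make plausible but the documents do not quantify.

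The effect is confined to descriptive safety tables. The primary ANCOVA, the MMRM and ANCOVA secondary analyses and the responder odds ratio are not affected. This is a small but real defect in a stated rule, and it is easily corrected.

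**What to change.** Add one sentence to SAP 3.1: for by-visit categorical summaries (laboratory and urinalysis shift, physical examination and, for consistency, ECG), the denominator is the number of subjects in the analysis set with a non-missing value at that visit, and also at baseline for shifts, with that n shown for each arm and visit.

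Keep population size for adverse event, hypoglycaemia, medication, disposition and any-time abnormality incidence tables.

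If the sponsor prefers to keep arm size in the by-visit tables, a missing row would at least make the remainder visible, but the percentages would still fall with dropout.

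The cost is that sentence and a denominator change in the affected table programs; no new data are needed. The change does not cure selection: subjects still measured at a late visit may differ from those who left, and the displayed n lets the reader judge that.
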